### **Bionic Pancreas Control Unit:**

The control unit consists of a stock iPhone 4S and a DexCom G4 Platinum receiver connected with a custom hardware interface and placed back-to-back in a custom enclosure. The G4 receiver converts the raw wireless signal from the transmitter into an estimated BG signal that is sent via a hardwired connection to the iPhone.

The iPhone runs iOS 6 in “Guided Access” mode, where the only app accessible to the subject is the Beta Bionics app, which runs the control algorithm. Access to other functions on the iPhone (namely, the home screen and the Settings app) is password protected and will be accessible to study staff personnel, but not to the subject. The control algorithm app has a graphical user interface (GUI) that displays the current CGM glucose, a graphical history of the CGM glucose, and doses of insulin and glucagon delivered by the control algorithm. The GUI can also be used to input meal announcements, designating the meal as larger than typical, typical in size, smaller than typical, or just a bite. This will trigger a partial meal-priming bolus the size of which will adapt during the course of the trial to meet a target of 75% of the insulin needs for that size of meal.

The GUI can also be used to manage open-loop control of meal boluses and correction boluses during periods when the CGM is offline, such as the period after a sensor is replaced and before the new sensor has been calibrated. During these times the control algorithm will determine and direct the administration of insulin basal rates, which can be temporarily scaled up or down or suspended by the user. The automatically selected basal rate will be either based on the volunteer's weight early in the course of the experiment, or on the average of adaptively determined basal rates for that time of day once sufficient experience has been accumulated (i.e. 24 hours or more) by the control algorithm.

The iPhone communicates wirelessly via the Bluetooth Low Energy (BTLE) protocol with two Tandem t:slim insulin pumps to deliver insulin and glucagon.

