#### **CGM Monitoring of Usual Care Days 1–6 (5 days):**

- An additional calibration will be performed by the study staff before breakfast and before study start at 3:00 PM using the HemoCue meter.
- A member of the study staff will be monitoring all volunteers in the usual care arm via telemetry around the clock. The staff monitoring telemetry will be able to communicate with camp healthcare providers by radio or cell phone and there will be a study “runner” on call to deal with any issues that may arise with functioning of study device or if telemetry staff is unable to contact the cabin camp healthcare provider.
- The G4 CGM system will be blinded to the volunteers and the high and low glucose alarms will be turned off. This will ensure that volunteers will not use this data to modify their BG control strategy. The screen of the bionic pancreas control unit will be locked except for access to enter BG values and all audible alarms will be silenced. The bionic pancreas worn by volunteers in the usual care arm will be streaming data to the SweetSpot cloud service for remote real-time monitoring by study staff, but it will not be controlling insulin or glucagon infusion.
- All BG values taken as a part of usual care will be entered into the bionic pancreas interface.
- The experimental period will begin at 3:00 PM on the first day of the camp session (Sunday).
- Over the next five days (3:00 PM Sunday to 3:00 PM Friday) volunteers will have their BG managed according to the camp’s health care manual. All BG measurements will be performed by study staff or camp healthcare providers with the HemoCue device. Study staff will calibrate the G4 before breakfast and before supper with the HemoCue BG meter.
- During the experiment the bionic pancreas device will be worn by the volunteer or kept nearby (such as when sleeping) at all times to ensure good radio-frequency signal reception. The device may be removed for short periods of time (no more than 30 minutes) for showering and swimming.
- If during the course of an experiment, a DexCom G4 sensor fails (reports sensor failure, ceases

to transmit data, reports multiple calibration failures, or reports questionable data) a new sensor will be inserted and calibrated.

- Volunteers who are counselors will have to remain on the camp grounds during their days off.
- There will be a camp health care provider assigned to each camp cabin throughout the usual care period.

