- If there is an interruption in the DexCom G4 CGM output the bionic pancreas will automatically switch to giving basal insulin based on historical basal insulin needs at that time of the day. If the failure occurs early in the experiment before 24 hours of historical data has been accumulated by the device, the basal rate will be primarily based on the volunteer's weight. In addition, any BG measurements entered into the bionic pancreas will be used to dose insulin and glucagon as if they were CGM values and the system will continue to accept meal announcements.
- If there is an interruption in the DexCom G4 CGM output, study staff will assist the volunteer in recovering CGM data streaming. This may involve forced calibrations or replacement of the sensor and calibration. Once it is back online, closed-loop BG control will resume automatically.
- If there is a complete failure of bionic pancreas operation, BG control will default to usual care camp protocol and subjects will use their own insulin pump (which will be stored by the study staff) until the bionic pancreas can be brought back online.
- The DexCom CGM will be calibrated each morning before breakfast and each evening before dinner using the HemoCue meter. IF it is a good time to calibrate. This will be determined by a decision support algorithm. A good time to calibrate means a rate of change in CGM glucose  $< |1|$  mg/dl/min, no glucagon boluses in the last 15 minutes, and no carbohydrate intake in the last 30 minutes. These conditions are intended to reduce the likelihood of performing a calibration when there are rapid changes in BG and when there are changes in BG that are not yet reflected in CGM glucose due to physiologic lag.
- Additional calibrations may be performed if the following criteria are met:
  - If the CGM reported value does not meet the ISO standard ( $< 15$  mg/dl difference for BG values  $< 75$  mg/dl,  $< 20\%$  absolute difference for BG values  $> 75$  mg/dL) at the time of the BG measurement AND it is a good time to calibrate according to the decision support tool (the CGM derivative is  $< 1$  mg/dl/min and there has been no carbohydrate intake in the last 30 minutes or glucagon boluses in the last 15 minutes) a calibration will be performed.

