  - If it is NOT a good time to calibrate, the difference between CGM glucose and BG may be due to the physiologic lag (roughly 15 min) between BG and interstitial fluid glucose, and this cannot be corrected by calibration. In this instance, a decision about performing an additional Hemocue BG check at the next good time to calibrate will be made by adjusting the ISO range to take into account the CGM trend. For example, if the CGM glucose is falling with a derivative of  $-2$  mg/dl/min and the BG is 100 mg/dl, the CGM glucose can be up to 130 mg/dl ( $100 \text{ mg/dl} + 15 \text{ min} * 2 \text{ mg/dl/min}$ ) without indicating the need to do

another BG check at the next good time to calibrate. If an additional BG check is indicated despite these correction factors, then at the next good time to calibrate a BG check will be performed and a calibration will be performed IF and ONLY IF the CGM is still not compliant with the ISO standard at the time of that additional BG check. This will avoid forcing extra calibrations when a large disparity between the CGM value and BG was due to the physiologic lag between BG and interstitial fluid glucose.

- At 3:00 PM on day 6 (Friday) the closed-loop portion of the experiment will end. Infusion sets and CGM sensor will be removed. Subjects will insert one of their own infusion sets and start their own basal insulin rate. Blood glucose control will then resume under usual care camp protocols.

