**VI. b. Study Endpoints**

**Co-primary endpoint analysis:**

- Difference in average BG between closed-loop and open-loop periods as determined from all scheduled HemoCue measurements. This mean will be evenly weighted across the daytime and nighttime hours.
- Difference between closed-loop and open-loop in the percentage of the above subset of BG values less than 70 mg/dl.

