**Secondary endpoint analyses - BG:**

- All of following metrics will be generated from the HemoCue data during the closed-loop period and the usual care period, and the difference between the two periods will be reported unless otherwise specified:
- Average BG as determined from all HemoCue measurements taken during the day/nighttime including all extra measurements taken before meals, taken during exercise, and taken for hypoglycemia monitoring.

- Percentage of the above subset of BG values less than 70 mg/dl.
- Average BG as determined from the pre-meal, before bed, 12:00 AM, and 3:45 AM HemoCue measurements (6measurements per day)
- Percentage of the above subset of BG values less than 70 mg/dl.
- Percentage of subjects with mean BG < 154 mg/dl using all BG values
- Difference in the percentage of subjects with mean BG < 154 mg/dl using before meal and before bedtime BG values only
- Percentage of study days with mean BG < 154 mg/dl
- Number of hypoglycemic events as determined from all HemoCue measurements
- Nadir BG for each hypoglycemic event as determined from HemoCue measurements
- Fraction of scheduled BG measurements within each of the following glucose ranges as determined from all HemoCue measurements :
  - < 70 mg/dl
  - 70-120 mg/dl
  - 70-180 mg/dl
  - >180 mg/dl
  - >250 mg/dl
- Risk of hypoglycemia and hyperglycemia >180 mg/dl and >250 mg/dl during hours with vs. without bionic pancreas downtime
- Difference of outcome measures on day 1 vs. remaining days (days 2-5) and on day 1-2 vs. on remaining days (days 3-5)
- Difference in average BG as determined from the pre-meal, before bed, and 12:00 AM measurements between the non-participants and the open-loop and closed-loop arms.
- Percentage of the above subset of BG values less than 70 mg/dl between the non-participants and the open-loop and closed-loop arms.
- Difference in the percentage of subjects with mean BG < 154 mg/dl using before meal and before bedtime BG values only between the non-participants and the open-loop and closed-loop arms.
- Number of hypoglycemic events as determined from all BG measurements
- Nadir BG for each hypoglycemic event as determined from BG measurements
- Fraction of scheduled BG measurements within each of the following glucose ranges as determined from all BG measurements :
  - < 70 mg/dl
  - 70-120 mg/dl
  - 70-180 mg/dl
  - >180 mg/dl
  - >250 mg/dl

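### Unscheduled HemoCue checks follow different written rules in the two periods, yet hypoglycemic events from all readings are compared with no allowance for the number of checks

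*Combined protocol and SAP*

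**What the plan says.** Section VI. b separates two kinds of endpoint. The co-primary mean BG is "as determined from all scheduled HemoCue measurements", and the co-primary percentage below 70 mg/dl uses the same readings. The secondary BG list adds a mean and a percentage below 70 mg/dl that include extra measurements, and "Number of hypoglycemic events as determined from all HemoCue measurements". That event count has no stated threshold, no rule for merging readings into one episode, and no adjustment for the number of checks. The CGM event count in the same section has both a threshold and a merging rule.

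Rules stated only for closed loop:
- Section V. d. iii describes an ISO re-check: when it is not a good time to calibrate, "a decision about performing an additional Hemocue BG check at the next good time to calibrate will be made by adjusting the ISO range", and "If an additional BG check is indicated despite these correction factors, then at the next good time to calibrate a BG check will be performed".
- The same section says study staff monitor in addition to camp staff once closed loop starts, and that study clinicians circulate with telemetry directing them to volunteers at risk of low or high glucose.
- Section V. c (HemoCue Blood Glucose Meter) sets at least seven readings a day for closed loop, and the camp schedule for usual care.

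Stated only under usual care: the usual-care part of V. d. iii allows extra daytime checks depending on the number of hypoglycemic episodes, or on the camp physician's order. For CGM calibration during the period it says "Study staff will calibrate the G4 before breakfast and before supper with the HemoCue BG meter". Its closed list of departures from camp practice contains no ISO re-check.

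For both periods, section VI. a lists additional HemoCue values as data collected, without the reason for the check.

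**The concern.** A low of limited duration enters a fingerstick count only if someone tests while it lasts. If one period has more checks, or checks timed differently, its count can differ with no true difference in hypoglycemia. The mean and percentage below 70 mg/dl behave differently: randomly timed extra checks leave them unbiased, but checks prompted by glucose level or by recent lows do not. At stake is whether a between-period difference in these secondary hypoglycemia results can be credited to the device.

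**Working it through.** **Step 1. Triggers side by side.**

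| Trigger for a HemoCue check | Closed loop | Usual care |
|---|---|---|
| Scheduled (meals, snacks, bedtime, midnight, 3:45 AM; VI. a) | yes | yes |
| Symptoms (V. e) | yes | yes |
| Nocturnal alert (V. d. iii) | yes | yes |
| Recheck 15–20 min after a mild low (V. e) | yes | yes |
| Lag-adjusted ISO re-check | yes | not stated |
| Floor of seven a day (V. c) | yes | camp schedule |
| Circulating study clinicians steered by telemetry | yes | not stated |
| Extra daytime checks driven by hypoglycemia | not stated | yes |

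**Step 2. How much each unequal row could add.**
- *ISO re-check.* If the CGM misses the limit at a good time to calibrate, the reading already taken is used and no new fingerstick follows. If it is not a good time, the limit is widened for lag. The protocol's own example is BG 100 mg/dl and CGM falling at 2 mg/dl/min, which allows a CGM value up to 100 + 15 × 2 = 130 mg/dl. Only a gap beyond that leads to another check. That check waits until CGM change is below 1 mg/dl/min, with "no glucagon boluses in the last 15 minutes, and no carbohydrate intake in the last 30 minutes". It is a real closed-loop trigger, but a narrow one, and it is deferred after treatment of a low.
- *Seven-a-day floor.* Three meals, a snack, bedtime, midnight and 3:45 AM already make seven if snack and bedtime are separate readings. The secondary list counts six from pre-meal, before-bed, midnight and 3:45 AM readings. The floor may add one reading or none.
- *Staff.* Closer observation could lead to more checks. The text gives no number.
- *Usual-care rule.* It adds readings after lows. Closed-loop volunteers otherwise follow camp guidelines, so it may apply there too, but the text does not say so.

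**Step 3. Illustration of sensitivity to the number of checks.** The plan gives no figure to reproduce. Assume n checks a day at random times and a low lasting d minutes. The probability of detection is 1 − (1 − d/1440)^n.

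| d (min) | n = 7 | n = 8 | ratio 8:7 | n = 9 | ratio 9:7 |
|---|---|---|---|---|---|
| 20 | 9.3% | 10.6% | 1.14 | 11.8% | 1.27 |
| 45 | 19.9% | 22.4% | 1.13 | 24.9% | 1.25 |
| 90 | 36.3% | 40.3% | 1.11 | 44.1% | 1.21 |

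One extra check every day adds 11–14%, and two add 21–27%. For very short lows the ratio approaches 8/7 = 1.14.

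**Step 4. Why this is not an estimate.** Section V. c expects one to two extra readings only on occasion, and relative to standard camp care, not to this trial's usual-care period. Part of that may be the 3:45 AM check, which both periods have. Two assumed scenarios show the effect:
- If one extra check falls on one day in five, the gain is 0.2 × 11–14%, or about 2–3%.
- If half of all lows are found anyway through shared triggers, one extra check every day gives, for d = 45, (0.5 + 0.5 × 0.224)/(0.5 + 0.5 × 0.199) = 0.612/0.600, or about 2%. For 20 and 90 minutes it is about 1% and 3%.

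**The case against.** The strongest reply is that the triggers aimed at hypoglycemia are shared. Symptoms, the nocturnal alert and the recheck after a low apply in both periods, as do round-the-clock telemetry and the scheduled readings. The section on potential benefits also describes intensive study-staff monitoring in both arms. The plan already has comparisons that do not depend on unscheduled checks: both co-primaries, a fixed six-a-day secondary analysis, and CGM event counts with time and area below 70 mg/dl. The event count is not named in the success criteria (VI. d). All of this stands, and it limits the point to a few secondary results.

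A second reply is that the reason for a check can be worked out later, because HemoCue, CGM, calibration and glucagon data are stored electronically (IX. a) and carbohydrate treatments are timed (V. e). This stands in part. Scheduled readings, rechecks and many ISO re-checks could probably be identified. A check prompted by symptoms and one prompted by a circulating clinician could not be told apart reliably.

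A reader might infer that lows are looked for harder in closed loop, so that the device is made to look worse. The documents do not establish this:
- The control unit "displays the current CGM glucose, a graphical history of the CGM glucose, and doses of insulin and glucagon delivered by the control algorithm", while in usual care "The G4 CGM system will be blinded to the volunteers and the high and low glucose alarms will be turned off". No text makes a displayed CGM value a reason for a HemoCue check.
- The rule before disconnecting for a shower gives a BG threshold, but it names no meter and orders no fingerstick.
- The ISO re-check is deferred after carbohydrate or glucagon, so it may catch few lows.
- A trigger driven by hypoglycemia is written under usual care.
- Camp rules require repeat checks at BG of 250 mg/dl or more, which add readings to whichever period runs higher.

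**Conclusion.** The point holds as an ascertainment difference in secondary endpoints. Written rules for unscheduled HemoCue checks differ between the periods, and the raw event count from all readings makes no allowance for it. A difference in that count, or in the all-readings mean and percentage below 70 mg/dl, cannot be attributed wholly to treatment, whichever period it favors. Direction and size are unknown. The 11–14% figure assumes one extra randomly timed check every day on top of seven and no detection by other triggers. Rarer extra checks or more shared detection bring it down to about 1–3% in the assumed scenarios shown. The co-primary endpoints and the CGM event counts do not use unscheduled HemoCue readings and are not affected. The change is worth making because it is cheap and concerns a hypoglycemia comparison in an unblinded crossover.

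**What to change.** 1. Add a field to the BG log giving the reason for each unscheduled HemoCue reading: symptoms, nocturnal alert, recheck of a low, ISO re-check, hyperglycemia recheck, staff decision, other.
2. Define a HemoCue hypoglycemic event by a stated threshold and an episode-merging rule in the spirit of the CGM rule. The CGM gap of under 15 minutes needs adapting, because rechecks come 15–20 minutes apart and could otherwise count one low twice.
3. Make the between-period event comparison on scheduled readings plus triggers common to both periods: symptoms, nocturnal alert and recheck of a low.
4. Keep the count from all readings, and the all-readings mean and percentage below 70 mg/dl, as supplementary results. Show checks per volunteer-day by period, and by reason, beside them.

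The cost is one log field and a few lines of analysis text. Some readings leave the main event count. No testing or treatment procedure changes.

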#### **V. e. Response to Hypoglycemia**

- All subjective symptoms of hypoglycemia will be investigated with a capillary BG using a HemoCue meter.
- Volunteers in both of the study arms (closed-loop and usual care) will take carbohydrates to treat hypoglycemia or symptoms consistent with hypoglycemia according to a protocol modified from the usual camp protocol as follows:
- Mild hypoglycemia (mild signs and symptoms or BG 60–80 mg/dl, able to self treat):
  - Wait 15–20 minutes and recheck BG
  - If BG is still < 70 give 15 gm of rapid-acting carbohydrates (glucose tabs, juice, milk, gel, etc.)
- The modified hypoglycemia protocol is intended to allow auto-treatment of mild hypoglycemia with glucagon by the control algorithm to occur without being preempted by carbohydrates given prior to the onset of hypoglycemia (for instance in the 70-80 mg/dl range) or when hypoglycemia is mild (BG 60-70 mg/dl). In order to maintain safety, a second BG check in 15-20 minutes is included so that hypoglycemia is treated if not averted by the closed-loop system.
- For experimental validity, the same modifications from camp policy need to be used for both the closed-loop and open-loop arms of the study. Note that treatment of BG < 60 mg/dl will be according to the normal camp protocol in both arms (immediate treatment with rapid-acting carbohydrates) AND subjects may take carbohydrates at any time for symptoms when BG is < 80 mg/dl
- Camp healthcare providers and camp counselors will carry rapid acting and complex carbohydrate interventions with them at all times. All carbohydrate treatments for hypoglycemia will be documented by study staff (amount and time).
- In any case in which two rapid-acting carbohydrate interventions must be administered by camp protocol or if glucagon is administered manually by injection, a study staff member will check the operation of the bionic pancreas system. Consideration will be given to replacing the glucagon infusion set and/or recalibrating the CGM.

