### **Secondary endpoint analyses – CGM:**

- All of following metrics will be generated from the DexCom G4 Platinum CGM data during the closed-loop period and the usual care period, and the difference between the two periods will be reported unless otherwise specified. Each of these measures will be calculated for the entire period and separately for the full day and for the nighttime (11:00 PM to 7:00 AM).
- Mean CGMG
- Number of CGMG events < 70 mg/dl (episodes separated by < 15 minutes will be considered a single episode) and nadir for each
- Fraction of time spent within each of the following glucose ranges:

- < 70 mg/dl
- 70-120 mg/dl
- 70-180 mg/dl
- >180 mg/dl
- >250 mg/dl
- Area over the curve and below 70 mg/dl (measure of total hypoglycemia exposure)
- Area over the curve and below 50 mg/dl (measure of significant hypoglycemia exposure)
- Percentage of subjects with mean CGMG < 154 mg/dl
- Percentage of study days with mean CGMG < 154 mg/dl
- Mean CGMG in the four hour period following meals
- Mean CGMG during exercise (more active periods, periods of activity greater than walking intensity based on accelerometer data)
- Number of incidents of hypoglycemia and nadir CGMG during exercise
- Correlation between exercise intensity (based on accelerometer data) and likelihood of a hypoglycemic event by CGMG
- Risk of hypoglycemia and hyperglycemia >180 mg/dl and >250 mg/dl during hours with vs. without bionic pancreas downtime (closed-loop period only)
- Mean absolute relative deviation (MARD) of CGM vs. scheduled HemoCue BG measurements
- Standard deviation of CGM values
- Standard deviation of CGM values at night (11:00 PM to 7:00 AM)
- MARD vs. all HemoCue BG measurements Additional accuracy measures using all of the HemoCue measurements as the standard. Statistics will include:
- Median, quartiles, and mean absolute relative difference (MARD) and mean absolute difference (MAD) between CGM and BG reported separately in hypoglycemic (< 70 mg/dl), normoglycemic (70-120 mg/dl), postprandial target (70-180 mg/dl), hyperglycemic (> 180 mg/dl and > 250 mg/dl) ranges.
- Pearson and Spearman correlation coefficient between CGM and BG values reported separately in each range (hypoglycemic, normoglycemic, hyperglycemic).
- Intercept and slope of best-fit line for CGM to BG correlation plots

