- Total number of grams of carbohydrate taken for hypoglycemia during the daytime ((7:00 AM – 11:00 PM)
- Number of carbohydrate interventions for hypoglycemia overnight (11:00 PM – 7:00 AM)
- Total number of grams of carbohydrate taken for hypoglycemia overnight (11:00 AM – 7:00 AM)

We will calculate means, median, percentages, standard deviations, standard errors, inter-quartile

ranges, and 95% confidence intervals in descriptive analyses. We will use paired t-test for comparison of means. We will use multivariate regression models with repeated measurements to compare means and percentages while adjusting for patient demographics characteristics (age, gender).

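### The per-event nadir endpoints compare the depth of lows only among lows that occurred, so their between-period difference can shrink, hide or reverse a real benefit

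*Combined protocol and SAP*

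**What the plan says.** In section VI. b., the list headed Secondary endpoint analyses - BG opens with a general rule that "the difference between the two periods will be reported unless otherwise specified". The list includes "Nadir BG for each hypoglycemic event as determined from HemoCue measurements". A second nadir item, "Nadir BG for each hypoglycemic event as determined from BG measurements", comes after the comparisons with non-participants. The CGM list carries the same general rule and includes "Number of CGMG events < 70 mg/dl (episodes separated by < 15 minutes will be considered a single episode) and nadir for each" and "Number of incidents of hypoglycemia and nadir CGMG during exercise". Nothing exempts the nadir items from the between-period rule.

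The methods paragraph at the end of VI. b. says "We will use paired t-test for comparison of means" and adds repeated-measures regression adjusted for age and gender. It gives no value or handling rule for a volunteer who has no low in a period.

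The plan also has measures that exist for everyone. The co-primary is "Difference between closed-loop and open-loop in the percentage of the above subset of BG values less than 70 mg/dl". The CGM list has time below 70 mg/dl and area below 70 and below 50 mg/dl. The lowest HemoCue range, however, is < 70 mg/dl.

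**The concern.** Which lows occur is itself a result of treatment. Section V. e. states the intent: "The modified hypoglycemia protocol is intended to allow auto-treatment of mild hypoglycemia with glucagon by the control algorithm to occur". If the device averts lows, and mild ones most of all, the lows left in the closed-loop period are a selected and probably deeper set. The crossover pairs volunteers, but it does not make these two sets of events comparable. A mean nadir per event can then stay flat or fall although volunteers have fewer and less severe lows. A volunteer with no low in one period has no nadir for the paired analysis, and those are the volunteers in whom prevention worked best.

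Depth matters here because the protocol itself grades it: the camp policy summary calls BG < 60 mg/dl moderate, and the description of the nocturnal alert system calls BG < 50 mg/dl significant. On the HemoCue, nadir is the only listed comparison that speaks to depth.

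**Working it through.** The plan states no figure to reproduce: section VI. c. says that the data for a formal power analysis are lacking. It gives no depth distribution, no prevention pattern and no usual-care rate of lows. All three are assumptions below. A low means BG < 70 mg/dl, and differences are closed-loop minus usual care, so a negative value makes closed-loop look worse.

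**1. Closed-form example.** Let depth below 70 be exponential with mean 12 mg/dl, so the usual-care mean nadir is 70 - 12 = 58.0.

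- *Every low raised by 10 mg/dl.* Lows remaining: exp(-10/12) = 43%. Lows with nadir < 50, as a share of the original lows: exp(-20/12) = 18.9% before and exp(-30/12) = 8.2% after, a 57% fall. Mean nadir of the remaining lows: still 58.0, a difference of 0.
- *80% of lows with nadir >= 60 averted, and 40% of deeper ones.* Retained: 0.2 × 0.565 + 0.6 × 0.435 = 0.374 of the lows. Mean depth is (12 - 0.435 × 22)/0.565 = 4.3 for mild lows and 10 + 12 = 22 for deeper ones. Mean depth of retained lows: (0.113 × 4.3 + 0.261 × 22)/0.374, about 16.7, so the mean nadir is about 53.3. Lows < 50 fall 40% (18.9% to 11.3%), yet mean nadir looks 4.7 mg/dl worse.

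**2. Other depth shapes.** The exact zero above is special to the exponential, which has no memory. Four shapes with mean depth about 10 mg/dl were simulated:

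| Depth shape | Every nadir raised 5: lows remaining | Total depth ratio | Nadir difference | 60% of mild, 30% of deeper averted: lows remaining | Total depth ratio | Nadir difference |
|---|---|---|---|---|---|---|
| Exponential | 0.61 | 0.61 | 0.00 | 0.51 | 0.62 | -2.16 |
| Half-normal | 0.69 | 0.58 | +1.61 | 0.53 | 0.62 | -1.72 |
| Gamma (shape 2) | 0.74 | 0.55 | +2.50 | 0.52 | 0.60 | -1.55 |
| Heavy-tailed mixture | 0.53 | 0.61 | -1.24 | 0.49 | 0.61 | -2.31 |

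Mild means nadir >= 60. A true 5 mg/dl gain is halved at best, and hidden or reversed in two shapes. In the right-hand scenario lows < 50 fall 30% in every shape, yet nadir always looks worse. Averting half the lows at random gives a difference of 0.00 in every shape. Total depth below 70, which scores a period without a low as zero, shows the benefit throughout.

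**3. Volunteers with a nadir in both periods.** With m independent scheduled checks and a proportion p < 70 mg/dl, P(at least one low) = 1 - (1 - p)^m. Six to seven checks a day for five days give m = 30 to 35.

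- p = 3% assumed in both periods, m = 30: 1 - 0.97^30 = 0.60, and 0.60² = 36%, or about 11 to 12 of 32.
- Closed-loop 0.4% (the higher of the two pediatric figures in section I. c.), usual care assumed 5%, m = 35: 0.131 × 0.834 = 0.109, or 3.5 of 32. With usual care at 2% or 10%: 2.1 or 4.1 of 32.
- Both at 5%, m = 35: 0.834² = 0.695, or about 22 of 32.

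Events are counted from all HemoCue readings, so scheduled checks alone understate these numbers. The spread shows how far the paired set depends on the rates.

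**The case against.** The strongest reply is that the nadir does not stand alone. Event counts are listed directly above it or in the same item, so in the first example a reader would see the count fall by 57%. Area below 70 and below 50 mg/dl by CGM is zero when there is no low and combines depth with duration. This stands, and a reader who inferred that the plan's assessment of depth rests on nadir alone would be wrong. What remains is that those areas come only from the CGM, which in the closed-loop period is the controller's own input.

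A second reply is that the plan names no mean nadir and no test on nadirs specifically, and that a per-event item has no single defined difference. The summary is indeed unspecified. But the general rule promises a between-period difference. Regression would let a volunteer with lows in one period contribute, and the selection would remain.

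Two stronger readings are tempting. One is that the device will look worse on nadir. That is not inevitable: with half-normal or gamma depths a uniform upward shift still shows, only reduced. The other is that shortening lows also biases nadir. For five-minute CGM, a shorter low of equal depth rightly leaves the nadir unchanged. For sparse HemoCue checks, a simulation that halved every duration barely moved the observed nadir (62.0 to 62.4, or 58.3 to 58.1 if deeper lows last longer). It fell by about 2 mg/dl only when mild lows alone were shortened. The point therefore rests on prevention of lows.

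**Conclusion.** The point holds for the secondary nadir items on HemoCue, CGM and exercise. Their between-period difference is conditioned on events that treatment changes, so it is not a randomised within-person contrast. Depending on the depth distribution and on which lows are averted, a real benefit can appear reduced, null or reversed; in the scenarios run, the differences ranged from +2.50 to -4.7 mg/dl. Those sizes rest on assumed depths and prevention patterns, and the pair counts also on assumed rates and independent checks.

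A reader might infer that the trial's main conclusions are at risk. The documents do not support that: neither the co-primary endpoints nor the success criteria in section VI. d. use nadir. The practical gap is narrower: the reference meter has no sound comparison of depth below 70 mg/dl.

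**What to change.** In section VI. b., BG and CGM lists:

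- Keep per-event nadirs as a descriptive listing, read beside event counts and CGM area below 70 and below 50 mg/dl. Drop their between-period difference.
- HemoCue: add the percentage of scheduled values < 60 and < 50 mg/dl per volunteer and period (0 if none).
- CGM: add the number of events with nadir < 60 and < 50 mg/dl per volunteer and period (0 if none).
- Compare these as pairs with zeros included.
- Do not base the comparison on a period minimum or event count from all HemoCue readings. Extra checks are prompted by lows, symptoms and the nocturnal alert system, so such measures depend on how often a volunteer is checked.

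The cost is wording only, since section VI. a. already collects the data. The downside is imprecision. At the assumed 3% of 30 scheduled readings in 32 volunteers there are 0.03 × 30 × 32 = 28.8 values < 70 mg/dl per period. If 18.9% of them were < 50, as in the first example, that is about 5 values. These comparisons should be reported with confidence intervals and not read as evidence of no difference.
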